1.2. Process and Intervention

Patients with kidney stones who will undergo ESWL were randomized into 2 groups. Group 1 was given allopurinol, and group 2 was given a placebo. Allopurinol 300 mg was administered orally for a total of 3 days, starting from the day before ESWL. Malondialdehyde (MDA), nitric oxide (NO), kidney injury molecule-1 (KIM-1) in urine were measured by technique quantitative double antibody sandwich direct ELISA before ESWL, continued two hours, and 24 hours after ESWL. Changes in the interlobar artery resistive index (RI) were assessed together with measurements of shear wave velocity (SWV) values in the renal focal zone before ESWL, followed by two weeks, and four weeks after ESWL.

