1.3. Safety Evaluation

If there was any drug side effects or serious adverse events(SAE), the subjects were reported to the ethics committee as soon as possible, less than 24 hours from the first time they were discovered, and actions were carried out as quickly as possible until the series of events ends. SAE was written in detail on the SAE form, including the following; when it was first discovered, the manifestation of the incident, the conditions before the incident, the handling of the event, and the outcome.

If the subject experiences side effects such as allergic reactions (redness of the skin, swelling of the eyes or mouth) and severe gastrointestinal disturbances (vomiting, diarrhea), the subject will be excluded from the analysis. The subject will also be excluded from the analysis if the subjects experience complications related to ESWL

procedure such as ureteral obstruction, pain (VAS > 5), or there were signs of infection. Subjects will be evaluated when visiting the hospital according to schedule, telephone contact, or by making a home visit.

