1.4. Sample Size

The Population of the study consisted of patients with kidney stones who will undergo ESWL. The sample size was calculated based on the statistical diagnosis of the study which is, comparative analysis of independent two groups. A total of 70 subjects were planned to be included in the study, 35 of which were intervention while the rest were placebo. Patients were randomly assigned to both groups in this study.

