1.5. Ethical Approval

Approval for the study was granted by the Research Ethics Committee Faculty of Medicine, Udayana University (Number: 1637/UN14.2.2.VII.14/LT/2020). Verbal and written informed consent was obtained from all subjects in the study.

Author Contributions

Conflict of Interests

The Authors have no conflict of interests to declare

Acknowledgements

The authors thank all those participated in this study.

Financial Disclosure

STATISTICAL ANALYSIS PLAN (SAP)

Data collected in this study were analysed statistically using SPSS for Windows software 25. Data were analysed by descriptive statistics to describe the characteristics of the subjects based on the treatment group and presented in the form of a distribution table. The compatibility of the variables on the numerical data scale uses the average comparison with the independent t-test. The categorical-scale variables used the proportion comparison with chi-square test. The limit value of significance was set at 0.05. The normality data assessment in this study is based on the central limit theorem, where the sample size in each group more than 30 makes the z distribution close to the t distribution and the data will be normally distributed. Bivariate and Multivariate analyses were performed using repeated measure ANOVA to control covariates. The value of the limit of significance is set to 0.05.

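### Repeated-measures ANOVA is named without a sphericity correction, a deciding contrast or a missed-visit rule, so the 0.05 level is not assured and partly observed patients are dropped

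*Combined protocol and SAP*

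**What the plan says.** The Statistical Analysis Plan (SAP) gives the longitudinal analysis one sentence: "Bivariate and Multivariate analyses were performed using repeated measure ANOVA to control covariates". The level follows: "The value of the limit of significance is set to 0.05". The software is named ("Data collected in this study were analysed statistically using SPSS for Windows software 25"), but not the procedure or the output line on which a decision rests.

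Protocol section 1.2 (Process and Intervention) sets the measurement times. The urine markers MDA, NO and KIM-1 are measured "before ESWL, continued two hours, and 24 hours after ESWL". The resistive index and shear wave velocity are measured "before ESWL, followed by two weeks, and four weeks after ESWL". Every outcome therefore has one pre-ESWL and two post-ESWL values.

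On size, section 1.4 says: "A total of 70 subjects were planned to be included in the study, 35 of which were intervention while the rest were placebo". The stated basis is "comparative analysis of independent two groups", with no effect size, SD, power or dropout rate.

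The documents do not say whether group, time or group-by-time tests treatment, whether two or three visits form the repeated factor, which covariates are meant, how non-sphericity is handled, or how a missed visit is handled.

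**The concern.** Two properties of classical repeated-measures ANOVA matter here.

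- **Sphericity.** The uncorrected F for group-by-time is exact only when all between-visit differences have the same variance. The urine samples are unequally spaced around an acute injury, so a wider spread at 2 hours is plausible and equal variances are doubtful. The group-by-time term is also a natural choice for the treatment test when the pre-ESWL value is one of the repeated levels, because the trial asks whether allopurinol changes the response to ESWL. If the corrected and uncorrected results are both available and neither is named in advance, the choice can be made after seeing the p-values.
- **Complete cases.** The method uses only patients with every visit. Someone scanned at 2 weeks but not at 4 weeks contributes nothing. With 70 patients the loss of precision could matter, and the result could be biased if missing a visit is related to outcome.

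**Working it through.** **Inputs from the documents.** 35 per arm (section 1.4), three measurements per outcome (section 1.2), level 0.05 (SAP). Two-sided testing is assumed. The documents give no SDs, correlations or missing-visit rates, so those below are assumptions shown as ranges.

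**The plan's own figures.** The 70 patients cannot be reproduced for lack of inputs. Solving backwards with d = (1.960 + 0.842) × √(2/35) gives 0.67 SD at 80% power, or 0.68 SD using the t distribution. The 0.05 level can be checked: under sphericity the simulated type I error is 0.049.

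**Type I error.** Sphericity is measured by ε = [tr(M)]² / [(k − 1) tr(M²)], where M is the double-centred covariance matrix and k = 3. ε = 1 means sphericity, and the minimum is 1/(k − 1) = 0.5.

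Example: SDs 1:2:1 with all correlations 0.5. The difference variances are
- pre to 2 h: 1 + 4 − 2(0.5)(1)(2) = 3
- 2 h to 24 h: 4 + 1 − 2(0.5)(2)(1) = 3
- pre to 24 h: 1 + 1 − 2(0.5)(1)(1) = 1

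Then tr(M) = (3 + 3 + 1)/3 = 2.333, tr(M²) = 3.611 and ε = 5.444/(2 × 3.611) = 0.754.

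Simulated rejection rates with no treatment effect (normal data, 40,000 trials per row, simulation error about 0.001):

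| Assumed pattern | ε | Uncorrected group-by-time | Greenhouse-Geisser | Multivariate | Between-group main effect |
|---|---|---|---|---|---|
| Equal SDs, correlation 0.5 | 1.00 | 0.049 | 0.047 | 0.050 | 0.051 |
| AR(1), 0.5 | 0.93 | 0.053 | 0.049 | 0.050 | 0.049 |
| AR(1), 0.7 | 0.88 | 0.055 | 0.048 | 0.050 | 0.050 |
| SD 1:2:1, correlation 0.5 | 0.75 | 0.062 | 0.049 | 0.050 | 0.049 |
| SD 1:3:1.5, correlation 0.4 | 0.71 | 0.066 | 0.050 | 0.052 | 0.049 |
| Correlations 0.9/0.2/0.2 | 0.60 | 0.076 | 0.050 | 0.050 | 0.049 |
| Near the lower bound | 0.52 | 0.083 | 0.050 | 0.050 | 0.048 |

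Further runs with correlations between 0.3 and 0.6 gave 5.9-7.0% for SD 1:2:1, 6.9-8.0% for 1:3:1 and 7.2-8.0% for 1:4:1.

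Ceiling at ε = 0.5: the uncorrected critical value is F₀.₉₅(2, 136) = 3.063, and P(F(1, 68) > 3.063) = 0.085.

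If only the two post-ESWL values are the repeated levels and the pre-ESWL value is a covariate, there is a single within-patient difference and sphericity cannot fail. Simulated type I error in that layout was 0.048-0.050 for SD 1:2:1, 1:3:1 and 1:4:1.

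**Complete cases.** If each post-ESWL visit is missed independently with probability p, the complete fraction is (1 − p)².

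| Assumed p | Complete per arm, 35(1 − p)² | Observed at a given visit, 35(1 − p) |
|---|---|---|
| 2% | 33.6 | 34.3 |
| 5% | 31.6 | 33.3 |
| 10% | 28.4 | 31.5 |
| 15% | 25.3 | 29.8 |

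At p = 10%, the difference detectable with 80% power in a two-sample comparison at one visit is about 0.76 SD with 28 per arm and 0.72 SD with 31.5. Equivalently, a difference that 35 per arm would detect with 80% power is detected with about 71% power at 28 per arm and 76% at 31.5. A mixed model gains a little more by borrowing from the correlated visit.

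**The case against.** A reader might infer that the plan breaks its own 0.05 level. The documents do not support that. Inflation needs three repeated levels, group-by-time as the treatment test, the uncorrected F as the decision line, and marked non-sphericity. The SAP states none of these and does not exclude a corrected or multivariate test, either of which holds the level. Its reference to covariates is compatible with using the pre-ESWL value as one, and then sphericity is not at issue. The between-group main effect is unaffected in every pattern. The 2- to 4-fold SD spread is assumed and concerns only the urine markers. Nothing in the documents suggests a similar spike for the resistive index or shear wave velocity. All of this stands.

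A reader might also infer a known and large loss from missed visits. No rate is given, and the fair comparison is complete cases with observed-per-visit data (0.76 against 0.72 SD), not with full data (0.68 SD). If the same 10% of patients missed both post-ESWL visits, 31.5 per arm would be complete and a mixed model on post-ESWL values would gain nothing. Section 1.3 provides for telephone contact and home visits, which may limit losses, although it does not say whether samples or scans could be obtained that way.

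Finally, section 1.3 states for listed side effects that "the subject will be excluded from the analysis", and does the same for listed ESWL complications. Bias from those removals arises under any model and belongs to a separate point.

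What remains is that the SAP leaves the choice open, and that the method it names discards partly observed patients by construction.

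**Conclusion.** The point holds as a specification gap with a modest, conditional consequence. If the uncorrected group-by-time F on three visits decides, type I error is about 6-8% under the assumed 2-hour SD patterns, 5.3-5.5% under the AR(1) patterns, and at most about 8.5% with three visits and 35 per arm. If a corrected test, the multivariate test, the between-group main effect or the two-post-visit layout decides, the level holds at about 5%.

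Dropping patients with a missed visit follows from the named method, but its size is unknown. The 10% illustration costs about 0.04 SD in detectable difference relative to using all values at a visit, and rests on independent missingness. The change is worth making because a better method is available for the same data.

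**What to change.** Replace the repeated-measures ANOVA sentence with text to this effect:

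> Each outcome is analysed by a linear mixed model for repeated measures on its two post-ESWL values. Fixed terms are arm, visit, arm-by-visit, the pre-ESWL value, its interaction with visit, and the other covariates, listed here by name. The within-patient covariance is unstructured, with Satterthwaite degrees of freedom. Every patient in the analysis set with at least one post-ESWL value is included. The treatment test is [one stated arm contrast per outcome: the arm difference at a named visit, or averaged over both visits], at 0.05.

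If repeated-measures ANOVA is kept as a supporting analysis, state that the Greenhouse-Geisser p-value is the one used.

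The model makes no sphericity assumption and uses partly observed patients. It still assumes that missed visits are explained by the observed data in the model, which the SAP should say.

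The cost is SAP wording and a run of a standard procedure on data the trial already collects. P-values may be slightly larger than from the uncorrected ANOVA. If results have already been seen, the change should be dated and reported as made afterwards. The exclusions from analysis in section 1.3 need their own correction, because this change leaves them in place.
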